4.2 Exclusion Criteria

Exclusion criteria:

- Significant chronic illness.
- Active infection or received antibiotics within 1 month of study enrollment.
- Use of OTC probiotic within 1 month of study enrollment.
- Chronic gastrointestinal disorders, such as ulcerative colitis or Crohn's disease.
- Allergy to eggs or lactose.
- Having undergone bariatric procedures or surgeries such as gastric banding or bypass.
- Pregnancy.
- Any condition that, in the judgment of the Investigator, would place a subject at undue risk by being enrolled in the trial or cause inability to comply with the trial.

4.3 Subject Recruitment and Screening

Subjects will be recruited from the Cleveland, OH area. Subjects will be recruited by several methods, including (but not limited to) posted advertisements, chart review, and personal interactions with patients in the cardiology outpatient departments at the

Cleveland Clinic Foundation. All advertising materials used for this study will be approved by the Cleveland Clinic IRB prior to dissemination.

4.4 Early Withdrawal of Subjects

Subjects may withdraw from the trial at any time and for any reason. Some possible reasons for early withdrawal include the following:

- Development of a medical condition or need for concomitant treatment that precludes further participation in the trial
- The investigator removes the subject from the trial in the best interests of the subject
- Development of an active infection or starting an antibiotic treatment regimen
- Study completion or discontinuation prior to participant completion
- Subject withdraws consent to continued participation in the trial

5.0 STUDY DRUG/BIOLOGIC

5.1 Description

Choline bitartrate and phosphatidylcholine supplements will be used in this study. These will be obtained from a commercial source and stored as below. Whole, hardboiled, prepeled eggs and egg whites will also be obtained from a commercial source and stored as below.

5.2 Treatment Regimen

For subjects in arms 1, 3, and 4, 500 mg choline bitartrate tablets will be given to be taken daily by mouth. Subjects will be asked to take two tablets each day, one in the morning and one in the evening, for a total of 1,000 mg daily. Subjects in arm 2 will not receive any choline tablets.

For subjects in arms 2 and 3, four pre-peeled hardboiled eggs will be given to be taken daily by mouth, two in the morning and two in the evening. Subjects in arm 3 will be asked to eat the hardboiled eggs in addition to taking the choline bitartrate tablets.

For subjects in arm 4, four pre-peeled hardboiled eggs will be given and subjects will be instructed to eat only the egg whites while discarding the egg yolks. Subjects will be asked to eat two egg whites in the morning and two egg whites in the evening. Subjects in arm 4 will be asked to eat the egg whites in addition to taking the choline bitartrate tablets.

For subjects in arm 5, 420 mg phosphatidylcholine capsules will be given to be taken daily by mouth. Subjects will be asked to take 6 capsules each day, 3 in the morning and 3 in the evening, for a total of 2,520 mg daily. Subjects in arm 5 will not receive any hardboiled eggs.

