1.0 BACKGROUND AND SIGNIFICANCE

The principal goal for the study is to examine whether there is a difference between the ingestion of choline through supplements versus choline found within eggs on plasma TMAO levels. We have previously shown that dietary intake of trimethylamines, including the choline group of phosphatidylcholine (PC), is mechanistically linked to cardiovascular disease risk and that the metabolism of these trimethylamine nutrients in humans is modulated by the intestinal microbes (gut microbes). Additionally, extensive animal studies link an essential role of gut microbiota to the metabolism of choline and the production of metabolites that promote / accelerate atherosclerotic processes (Wang et al, 2011, Nature). We have also recently shown a 10-fold increase in plasma TMAO levels following supplementation with choline bitartrate supplements. However, another pilot study by a collaborator did not show the same increase in plasma TMAO levels following the ingestion of whole eggs, a major dietary source of choline. Therefore, with this study we wish to examine the differences, if any, between the ingestion of an equivalent mass of total choline in the free form (as bitartrate salt) as a supplement vs. within whole eggs. We also wish to examine the ingestion of an equivalent mass of choline as a phosphatidylcholine (PC) supplement capsule and compare this to the ingestion of the choline bitartrate supplements and/or the whole eggs.

Eggs, and specifically the egg yolk, contain a large amount of total choline (USDA Database for the Choline Content of Common Foods, 2008). However, egg white contains potential antimicrobial peptides that could influence gut microbial composition and function, and therefore impact conversion of choline into TMA and TMAO observed in subjects. Therefore, we hypothesize that the consumption of whole eggs (hardboiled) will not elevate plasma TMAO levels to the same extent as a comparable amount of total choline ingested in capsule form as the choline bitartrate salt. We further hypothesize that the consumption of egg white with choline bitartrate tablets may result in less of a rise in TMAO levels than ingestion of the choline bitartrate supplement alone.

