3.0 STUDY DESIGN

This is a prospective non-blinded randomized study with 5 study arms as detailed below. For each study arm, subjects will be asked to consume choline bitartrate tablets, phosphatidylcholine capsules, and/or eggs or egg whites every day for 4 weeks.

Arm 1: whole hardboiled egg

Arm 2: choline bitartrate tablets

Arm 3: whole hardboiled egg + choline bitartrate tablets

Arm 4: egg whites + choline bitartrate tablets

Arm 5: phosphatidylcholine capsules

For arms 1-4, subjects will be randomly assigned to one of these study arms at the time of enrollment. For arm 5, the phosphatidylcholine arm, which we have added in version 1.2 of this protocol, subjects will not be randomized but will instead be assigned this arm until at least 10 subjects have completed this arm. We expect to enroll at least 10 subjects into each of the 5 arms of the study, up to a maximum of 100 total study participants. The large anticipated maximum enrollment accounts for any subjects who may withdraw early or who may need to be withdrawn because of antibiotic usage or non-compliance during the course of the study.

At the first (baseline) study visit, subjects will have blood and urine samples collected. Subjects will then be randomized or assigned to one of the five study arms as described above.

Following randomization, or assignment in the case of arm 5, subjects will be asked to pick up their assigned study food and/or supplements each week. Spot urine collections will be collected weekly. Subjects will also be asked to provide a stool sample at the time of the spot urine collection if they are able to. The stool samples will be optional, we will not require them.

At the day 7 visit and the final visit they will have repeat blood and urine collections. After 4 weeks of supplementation, subjects will have their final study visit. This visit will occur between 26 and 30 days after their baseline visit.

	Day 1 (Baseline)	Day 2	Day 7*	Day 8	Day 14*	Day 21*	Day 28*	Final Visit (Day 29)
Informed consent	Х							
Vital signs and brief medical history	Х		Х				Х	
Fasting Blood Draw	Х		Х				Х	
Pick up eggs and/or supplements		Х	Х		Х	Х		
Spot Urine sample	Х		Х		Х	Х	Х	
Start 24 hour urine	Х		Х				Х	
Return 24-Hour Urine		Χ		Х				Х

|--|

^{*}these study visits can occur +/- 2 days from day noted

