6.0 STUDY PROCEDURES

This is a prospective pilot study consisting of 5 arms. Up to 100 subjects will be enrolled across all arms in this pilot study, with a goal of having at least 10 subjects complete each arm of the study.

Arm 1: Choline Bitartrate Tablets Alone

Subjects in this arm will be asked to take two 500mg choline bitartrate tablets (for a total of 1,000mg) daily by mouth for four weeks. They will be asked to take one capsule in the morning and one in the evening. We aim to have at least 10 subjects complete this arm.

Arm 2: Whole Hardboiled Eggs

Subjects in this arm will be asked to eat four hardboiled eggs daily for four weeks. They will be asked to eat 2 eggs in the morning and 2 eggs in the evening. We aim to have at least 10 subjects complete this arm.

Arm 3: Whole Hardboiled Egg + Choline Bitartrate Tablets

Subjects in this arm will be asked to eat four hardboiled eggs and take two 500mg choline bitartrate tablets (for a total of 1,000mg) by mouth daily for four weeks. They will be asked to eat 2 eggs and take 1 capsule in the morning, and then eat 2 eggs and take 1 capsule in the evening. We aim to have at least 10 subjects complete this arm.

Arm 4: Egg Whites + Choline Bitartrate Tablets

Subjects in this arm will be asked to eat the equivalent of four egg whites and take two 500mg choline bitartrate tablets (for a total of 1,000mg) by mouth daily for four weeks. They will be asked to eat 2 egg whites and take 1 capsule in the morning, and then eat 2 egg whites and take 1 capsule in the evening. We aim to have at least 10 subjects complete this arm.

Arm 5: Phosphatidylcholine Capsules Alone

Subjects in this arm will be asked to take six 420 mg choline bitartrate tablets (for a total of 2,025 mg) daily by mouth for four weeks. They will be asked to take three capsule in the morning and three in the evening. We aim to have at least 10 subjects comlete this arm.

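### Arms 1 and 2 are defined as eggs and choline tablets in section 3.0 but the other way round in sections 5.2 and 6.0, so the main contrast can be dispensed or analysed with its sign reversed

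*Combined protocol and SAP*

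**What the plan says.** Three sections of the combined protocol and SAP assign treatments to arm numbers.

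- **Section 3.0 (Study Design)** lists "Arm 1: whole hardboiled egg" and "Arm 2: choline bitartrate tablets", then says that subjects are randomised among arms 1 to 4 of that list.
- **Section 5.2 (Treatment Regimen)** gives the tablets to a different set of arms: "For subjects in arms 1, 3, and 4, 500 mg choline bitartrate tablets will be given to be taken daily by mouth". It adds "Subjects in arm 2 will not receive any choline tablets", and it assigns the whole eggs as follows: "For subjects in arms 2 and 3, four pre-peeled hardboiled eggs will be given to be taken daily by mouth".
- **Section 6.0 (Study Procedures)** uses the headings "Arm 1: Choline Bitartrate Tablets Alone" and "Arm 2: Whole Hardboiled Eggs", with doses and schedules to match.

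Section 1.0 states the principal goal, which is to "examine whether there is a difference between the ingestion of choline through supplements versus choline found within eggs on plasma TMAO levels".

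**The concern.** A randomised arm must mean one treatment wherever the protocol mentions it. Here the section that defines and randomises the arms contradicts the two sections that tell staff what to hand out. The conflict falls on the two arms that form the principal comparison.

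A swap applied consistently from allocation through to the analysis label would do no harm. The damage comes when two steps in that chain rely on different sections. Suppose arms are allocated and labelled from 3.0 while product is dispensed from 5.2. Every subject labelled as egg has then taken tablets, and every subject labelled as tablets has eaten eggs, so the estimated difference has the wrong sign. If staff or data handlers use the sections inconsistently, the difference shrinks toward zero instead.

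**Working it through.** **The mapping, side by side.** The plan gives no figure on this point to reproduce, so the check is a comparison of the text.

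| Section | Arm 1 | Arm 2 |
|---|---|---|
| 3.0 Study Design | Whole eggs | Choline bitartrate tablets |
| 5.2 Treatment Regimen | Choline bitartrate tablets | Whole eggs, no tablets |
| 6.0 Study Procedures | Choline bitartrate tablets | Whole eggs |

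Sections 5.2 and 6.0 agree with each other, and both reverse 3.0. Arms 3, 4 and 5 carry the same labels in 3.0 and 6.0. Each mapping is written out in words in current text, so this is neither an extraction fault nor a difference from superseded wording. No section says which numbering takes precedence.

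**Whether a majority of sections settles it.** It does not. Section 6.0 has errors of its own in Arm 5: it calls the capsules choline bitartrate tablets and totals six of 420 mg as 2,025 mg, whereas 6 × 420 = 2,520 mg, the figure in 5.2. Section 3.0 includes the Arm 5 text introduced in version 1.2, so it cannot be set aside as stale.

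**Whether the stated safeguards would catch a swap.**

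- Observed dosing (5.3) covers the first few visits and is there to confirm that subjects can comply. It does not describe checking the product against the allocation.
- The weekly urine check (5.3) looks for levels falling below baseline. Both products supply choline, so it would not tell the two arms apart.
- The accountability record (5.5) logs supplements. No log for eggs is described.
- The statistical methods (7.2) define no treatment coding, and 8.2 rules out a DMC and interim analyses.

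**Size of the effect on the estimate.** Let m_C and m_E be the mean log responses to choline tablets and eggs. Let q₁ be the fraction of subjects labelled egg who took tablets, and q₂ the fraction labelled tablets who ate eggs. The expected labelled difference is

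[(1 − q₂)m_C + q₂m_E] − [(1 − q₁)m_E + q₁m_C] = (1 − q₁ − q₂)(m_C − m_E).

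With equal crossing, q₁ = q₂ = q, the multiplier is 1 − 2q.

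Inputs:

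- The 10-fold rise on choline bitartrate is from section 1.0.
- A 1-fold (no change) response to eggs is an assumption. Section 1.0 says only that a pilot with eggs did not show the same increase.
- The values of q are illustrative.

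The true log difference is then ln(10) = 2.303.

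| q | 1 − 2q | Log difference | Apparent ratio |
|---|---|---|---|
| 0 | 1.0 | 2.303 | 10-fold |
| 0.1 | 0.8 | 1.842 | about 6.3-fold |
| 0.2 | 0.6 | 1.382 | about 4.0-fold |
| 0.5 | 0 | 0 | no difference |
| 1 | −1 | −2.303 | 10-fold in the wrong direction |

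For any other true ratio R, the apparent ratio is R^(1 − 2q). Section 6.0 aims for at least 10 completers per arm; at exactly 10, one crossed subject in each arm is 1/10, which is q = 0.1.

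**The case against.** The best reply is that this is an ordering slip in two lines of section 3.0, with little practical risk. The two sections that give doses and schedules agree, and nobody could dispense from 3.0 alone. The study is open-label, and eggs cannot be mistaken for tablets. The supplement log separates an arm that takes tablets from one that does not. The goal and hypotheses are stated by product, and the statistical methods use no arm numbers. Nothing describes the randomisation list or database coding, so coding by number alone is an inference. The values of q have no source, and a numbering conflict is more likely to give all-or-nothing mislabelling than a partial fraction.

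Much of this stands. No reversal is shown to have occurred, the attenuation table does not estimate this trial's risk, and a complete swap would contradict the hypothesis and might be noticed. What the reply does not do is remove the contradiction. Section 3.0 randomises among numbered arms, 5.2 identifies who receives what by arm number alone, and no described procedure compares the product handed out with the allocation. All-or-nothing mislabelling is also the worse outcome, because it reverses the sign. The supplement log can expose a swap, but only if someone compares it with the allocation, and the plan does not ask for that.

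**Conclusion.** The concern holds. Followed literally, the protocol gives opposite treatments for the same arm number in the two arms of its principal comparison, and nothing in it resolves the conflict. A complete mismatch between label and product reverses the sign of the egg-versus-choline difference. A partial one multiplies the expected log difference by 1 − 2q, assuming equal crossing in both arms; the fold-change figures rest further on the assumed 10-fold versus 1-fold contrast. The textual finding depends on none of these assumptions and does not rely on the sample-size calculation. The claim is that reversal is possible, not that it happened. It must be corrected because the consequence is severe and the remedy is cheap.

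**What to change.** 1. Replace the separate arm descriptions in 3.0, 5.2 and 6.0 with one treatment table giving arm number, product, dose and schedule, and have every section refer to it.
2. Choose the numbering by checking the randomisation list and dispensing records. The documents alone do not show which is right.
3. Carry the product name as well as the arm number in the randomisation list, REDCap and the analysis dataset. The documents do not say whether this is already done.
4. Before analysis, check each enrolled subject's assigned arm against the accountability record. Of these two arms, one should have supplement entries and the other none.

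The cost is a short amendment and a one-time check of existing records, with no extra patients or procedures.

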5.3 Subject Compliance Monitoring

Subjects will be observed taking their assigned treatment, either eggs or choline supplements, by a study coordinator or other study personnel during their first few visits to ensure the subjects are able to comply with the study procedures. Following this, weekly spot urine collections will be analyzed for choline, phosphatidylcholine (PC),

TMAO, TMA, crotonobetaine, and gammabutyrobetaine levels to ensure that subject levels do not drop from baseline, which would indicate non-compliance with the study treatments.

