2.0 STUDY OBJECTIVES

To compare the blood and urine levels of free choline, phosphatidylcholine (PC), trimethylamine-N-oxide (TMAO), trimethylamine (TMA), and gammabutyrobetaine in subjects before versus following the ingestion of choline provided in either the bitartrate salt (in supplement) form, within phosphatidylcholine (in supplement form), within eggs (whole or in part), or in combinations of these.

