3.1 Study Endpoints

- Baseline plasma and urine fasting choline, phosphatidylcholine (PC), trimethylamine-Noxide (TMAO), trimethylamine (TMA), crotonobetaine and gammabutyrobetaine levels.
 - Changes in levels of non-labeled TMAO, TMA, crotonobetaine, betaine and gammabutyrobetaine over time measured by established techniques by mass spectrometry.
 - Baseline and subsequent (end of study blood draw) changes in platelet function during study.
- Serial changes in plasma and urine (area under curve and percent rise calculations).
 - Correlation with baseline fasting choline, phosphatidylcholine (PC), TMAO, TMA, crotonobetaine and gammabutyrobetaine levels.
- Changes in markers of metabolism (e.g. lipid profile, and other metabolic markers).

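### Section 5.3 reads a fall below baseline in spot-urine outcome analytes as non-compliance; the inference is unsound, and removing subjects on a TMAO flag would shrink the arm contrasts

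*Combined protocol and SAP*

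**What the plan says.** Section 5.3 has two parts. At the first few visits, "Subjects will be observed taking their assigned treatment, either eggs or choline supplements, by a study coordinator" or other study staff. After that, weekly spot urine is analysed for choline, phosphatidylcholine (PC), TMAO, TMA, crotonobetaine and gammabutyrobetaine "to ensure that subject levels do not drop from baseline, which would indicate non-compliance with the study treatments". It gives no size of drop, no number of visits, no rule for combining the six analytes and no consequence.

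The same analytes are outcomes. The objective in section 2.0 is "To compare the blood and urine levels of free choline, phosphatidylcholine (PC), trimethylamine-N-oxide (TMAO), trimethylamine (TMA), and gammabutyrobetaine" before and after ingestion. Section 3.1 lists "Changes in levels of non-labeled TMAO, TMA, crotonobetaine, betaine and gammabutyrobetaine over time", which adds crotonobetaine, and "Serial changes in plasma and urine (area under curve and percent rise calculations").

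Section 3.0 sets the enrolment ceiling partly to allow for subjects "who may need to be withdrawn because of antibiotic usage or non-compliance during the course of the study". Section 4.4 does not name non-compliance among its possible reasons for withdrawal. Section 7.2 names no analysis population and does not say how flagged subjects are handled. Supplements are logged when dispensed and returned (5.5, 5.6); no such count is described for eggs.

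**The concern.** Adherence is judged by the response that the trial is meant to measure, and the arms are expected to differ in that response. Section 1.0 cites a 10-fold plasma TMAO rise with choline bitartrate and hypothesises that "consumption of whole eggs (hardboiled) will not elevate plasma TMAO levels to the same extent as a comparable amount of total choline" taken as bitartrate. It expects PC capsules to behave like eggs. A check that expects levels to hold above baseline is passed almost automatically in a strongly responding arm, and often failed by chance in a weakly responding one.

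If failing the check led to removal, the weakly responding arms would keep mainly subjects whose baseline happened to be low, and their rise would be overstated. The comparisons of eggs and PC with bitartrate, which are the purpose of the trial, would be pulled together. Section 6.0 aims for at least 10 completers per arm, so removed subjects could be replaced and the selection would not show in the final numbers.

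**Working it through.** The plan has no figure of its own to reproduce here: section 5.3 gives no threshold or error rate, and the 5 per arm in section 7.1 is not in dispute.

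**Inputs from the documents.** Baseline spot urine is collected before assignment, with follow-up at days 7, 14, 21 and 28 (3.0: "Spot urine collections will be collected weekly"). The expected bitartrate effect on plasma TMAO is 10-fold; the egg and PC effects are smaller, with no size given (1.0). Day 28 is the last blood draw, so a flag then could lead only to exclusion from analysis. That leaves three checks that could lead to withdrawal, or two if day 7 is still covered by observed intake.

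**Assumed inputs.** Within-subject SD s of ln TMAO 0.3-0.7, independent normal deviations, and plasma-urine correlation rho from 0 to 0.8. The documents give none of these.

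**Step 1: direction.** With other intake unchanged, a non-taker's follow-up levels vary around baseline. Non-compliance predicts no rise; it does not predict a fall.

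**Step 2: flag rate when the product has no effect on TMAO.** Baseline and k follow-up values are then exchangeable, for takers and non-takers alike. No drop occurs only if baseline is the lowest of k + 1 values, so P(at least one drop) = k/(k + 1): 2/3 = 67%, 3/4 = 75%, 4/5 = 80%. For the mean of the checks, P(drop) = 50% with symmetric errors. Neither result depends on s.

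**Step 3: flag rate when the product works.** For a true fold rise f and the mean of k checks, P(drop) = Phi(-ln f / (s x sqrt(1 + 1/k))). With f = 2 and k = 2 this is 0.03 at s = 0.3 and 0.21 at s = 0.7. The any-drop rates for compliant subjects come from simulation.

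| True rise | Any drop, 2 checks | Any drop, 3 checks | Mean drop, 2 or 3 checks |
|---|---|---|---|
| None | 67% | 75% | 50% |
| 2-fold | 9-37% | 12-45% | 2-21% |
| 10-fold | 0-3% | 0-3% | not tabulated |

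Non-takers in any arm have the rates in the first row, so at 2-fold the flag does carry some information.

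**Step 4: effect of removing flagged subjects (one illustration).** Take no true effect and checks at days 14 and 21. Retained subjects have a baseline urine deviation averaging -c x s, with c = 3/(2 sqrt(pi)) = 0.846 for any drop (baseline is the lowest of three) and c = sqrt(2/pi)/sqrt(1.5) = 0.651 for a drop in the mean. The false day-28 rise is exp(rho x c x s) in plasma and exp(c x s) in spot urine.

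- Plasma, rho = 0: 1.00-fold.
- Plasma, rho = 0.5-0.8: lowest exp(0.5 x 0.651 x 0.3) = 1.10, highest exp(0.8 x 0.846 x 0.7) = 1.61.
- Spot urine: lowest exp(0.651 x 0.3) = 1.22, highest exp(0.846 x 0.7) = 1.81.

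At a true 10-fold rise almost nobody is removed and the retained plasma fold is 10.0-10.2.

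**Step 5: other ways to combine the six analytes (two checks).** With uncorrelated analytes and no effect, any-of-six flags 1 - (1/3)^6 = 0.999. If only TMAO rises 10-fold and is never flagged, it flags 1 - (1/3)^5 = 0.996. With inter-analyte correlation up to an assumed 0.5, the lower ends are 0.950 and 0.937. All six falling at the same check flags 2 x (1/2)^6 - (1/3)^6 = 0.030 when uncorrelated and up to 0.24 when correlated. Removal under that rule gives a false plasma rise of only 1.00-1.13-fold (rho 0.2-0.8).

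**The case against.** The strongest reply is that the bias depends on steps the plan never states. Section 5.3 attaches no action to a drop. Section 3.0 mentions non-compliance only to explain the enrolment ceiling, section 4.4 does not list it, and section 7.2 excludes nobody. This stands: a flag that only leads to a conversation causes no selection. But section 5.3 is the only place that says what indicates non-compliance, section 3.0 foresees withdrawal for it, and nothing protects a flagged subject.

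Second, the plan expects a smaller TMAO rise with eggs and PC, not none. This also stands. At a true 2-fold rise the mean-drop flag separates takers (2-21%) from non-takers (50%), and retained subjects show a plasma rise of 2.02-2.58 instead of 2.00 at rho 0.5-0.8. The distortion shrinks but does not vanish, and it still differs between arms.

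Third, the main contrast would survive. At the unfavourable corner (SD 0.7, correlation 0.8, any drop) a true bitartrate-to-egg plasma ratio of 10 would show as about 6.4. That is correct, and the bias works against the trial's hypothesis, so it would not create a false positive. It would still misstate the size of the difference.

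Fourth, choline and PC relate more directly to intake than TMAO does, and urine is the only continuing check described for eggs. That is a reason to keep the measurements and not to forbid their use altogether. It does not make a fall below baseline evidence of non-compliance.

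**Conclusion.** The point holds, in two parts of different strength. The inference in section 5.3 is wrong as written: a fall below baseline is not what non-compliance predicts, and where a product leaves TMAO unchanged a TMAO flag cannot tell takers from non-takers. The 67%, 75% and 80% rates need only exchangeable visits, and the 50% rate only symmetric errors.

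The bias in the arm contrasts is conditional. It needs TMAO to drive the flag, flagged subjects to be withdrawn or excluded, and a small egg or PC effect on TMAO. Under those conditions, weakly responding arms lose far more compliant subjects than a 10-fold arm. With no true effect, the false plasma rise is 1.00-fold at zero plasma-urine correlation and 1.10-1.61-fold at 0.5-0.8. These are illustrations under assumed SDs and correlations, not bounds.

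The result also depends on the unstated combining rule. Any-of-six flags about 94-99.9% of subjects whether or not TMAO rises; it is uninformative and, with removal, would empty the arms. All-six-fall flags few and does little harm.

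A reader might infer that the protocol orders removal on the urine result, or that it predicts no TMAO effect of eggs or PC, and so that the comparison is certain to be biased. The documents support neither premise. This should be fixed because the repair is cheap and the exposed contrast is the main one.

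**What to change.** In section 5.3, replace the closing clause that equates a drop with non-compliance by: *a drop prompts a conversation about adherence and is not in itself evidence of non-compliance.*

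In sections 5.3 and 7.2 add: *No subject is withdrawn, replaced or excluded from the main as-assigned analysis for non-compliance solely on the basis of spot-urine analyte levels; removals under section 4.4 are unaffected. Any analysis excluding subjects on these levels is a sensitivity analysis.*

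Judge adherence from the observed intake already in section 5.3 and the supplement log in sections 5.5 and 5.6. A weekly question on egg intake is optional; it would cover the product that the log does not.

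The cost is one clause changed and a short statement added in two sections. Urine collections and the log stay as they are. The downside is that some non-compliance, mainly with eggs, will be missed, which slightly dilutes differences between arms.
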